3. A limited control set using listening to oral reading of the lyrics and silent reading of the written lyrics with observation of pointing to written lyrics (no music).

Dependent Variables:

The dependent variable was defined as silent reading/comprehension of targeted words/phrases by pointing to words/phrases in a phrase completion exercise without music. The dependent variable was kept constant for all three conditions.

Dependent Measures

Measurement of the dependent variable consisted of both direct systematic observational recording (DSOR) and treatment record video (for reliability/procedural fidelity assessment) of percentage correct over time (including follow-up) and trials- or sessions-to-criterion.

Research Design

An AATD was used for comparison of two separate but similar conditions when the effects may be non-reversible (see Gast & Ledford, 2014, pp. 324-332). Time between sessions was at least a day.

“Criteria:

1. Behaviors must be non-reversible—the behaviors will continue to be performed after instruction has stopped.
2. Behaviors should not be in the participants' repertoire.
3. Behaviors must be independent, meaning one behavior set/chain can be acquired without influencing performance on other behavior sets/chains.
4. Behaviors also must be functionally equivalent, meaning behaviors are likely to be influenced by the same environmental variable (e.g., the instructional strategies being studied).
5. *Behavior sets/chains must be of equal difficulty.* The dependent variable in this investigation will be phrases acquired, but three different sets will be required to fulfill the requirement that the behaviors are independent. To ensure that they are of equal difficulty, they must all be assessed for word complexity at a minimum.

Randomizing items between treatment conditions should result in a relatively equal distribution of difficulty” (Romer, Billingsley, & White (1988).

Procedures

All songs were pretested for familiarity and positive valence by questioning the participants (i.e. Do you know this song? Do you like it?). Response data was recorded. All songs perceived as not liked were eliminated and substitutions made; the new songs were then also pretested for familiarity and positive valence. Songs that were not familiar but were liked were noted but not changed.

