During the intervention (B), each song (music with lyrics) from set 1 (B1) was played in its entirety. When the targeted verse or chorus played, the written lyrics were simultaneously shown along with the song lyrics. The SLP pointed to the words of the targeted verse/chorus which was silently observed by the participant as they were sung. This was repeated for all ten songs. The phrase completion task was then presented, including the total 25 phrases, without music. The participant silently or orally read the phrase and circled the phrase completion choice. Correct responses were randomly verbally reinforced. Error responses were followed by verbal modeling and pointing to the correct choice by the SLP. The next session, each song (music with lyrics) from set 2 (B2) was played in its entirety. After the song played, the written lyrics from the targeted verse or chorus were presented. The SLP pointed to the words of the targeted verse/chorus which was silently observed by the participant. This was repeated for all ten songs. The phrase completion task was then presented, including the total 25 phrases. The participant silently or orally read the phrase and circled the phrase completion choice. Correct responses were randomly verbally reinforced. Error responses were followed by verbal modeling and pointing to the correct choice by the SLP. This was repeated for all ten songs. For all interventions, the number of correct responses were tallied on a LaPoint Base 10 form and the percent correct entered on the graph for that day. The same procedures were repeated, alternating procedures on sets 1 and 2 on subsequent treatment visits, until a criterion of 9/10 (90%) x 3 consecutive visits was reached on both sets. It was predetermined that if the criterion was not reached on one of the intervention sets, defined as no increase in percentage correct x 3 consecutive visits, that intervention would be considered to be limited in effectiveness and discontinued. Every third session was digitally recorded for a reliability check by the trained assistant. When both of the sets (B1 and B2) had been acquired or one acquired and the other discontinued, the number of sessions to criterion were counted for each intervention.

Potential Threats to Internal Validity

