Potential threats to internal validity included multiple-treatment interference in the form of sequential confounding and carryover effects. Counterbalancing conditions was necessary, and any carryover effects identified (see Gast & Ledford, 2014, chapter 5 p.101). Because AATD studies test efficiency, the goal involves demonstrating optimal performance as opposed to artificially deflated performance, so responses were reinforced during the baseline phase (see Gast & Ledford, 2014, p. 326).

Potential threats to internal validity also included possible history or maturation effects. A control set was used to rule out history and maturation effects.

Outcome Measures and Time Points

Pretest/post-test information on the ICF Body Functions/Structures, Activities, and Participation was provided (Hurkmans et al. 2011). The Boston Diagnostic Aphasia Examination (BDAE) (Goodglass, Harold, & Kaplan, 1983) was used as an outcome measure of reading acquisition. The BDAE is a classic anatomically-based diagnostic instrument. Because various components of language function may be selectively damaged by CNS lesions, results indicate the neuro-anatomical organization of language and localization of the lesion. Thus it serves as an appropriate assessment for research exploring neurological organization in the brain. Pretest reading scores on selected subtests from the BDAE full version were completed prior to baseline A and initiating intervention, and immediately following completion of intervention to assess generalization to non-trained stimuli. At four weeks follow-up the trained stimuli from all three interventions was retested to assess retention. The dependent variables, that is differential response to the two interventions (counted as the percent correct responses per day, a ratio scale which has equal intervals and an absolute zero, which allows for multiplication and division so is appropriate for averages), number of sessions required to achieve mastery at each level (simple counting but also a ratio scale as it has equal intervals and an absolute zero which allows for multiplication and division so allows for the difference between means), retention of the material (number of items remembered, another simple count which is also a ratio scale as it has equal intervals and an absolute zero and allows for the difference between means), was assessed using data analysis as described below.

Data Analysis

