The role of the primary investigator presents the possibility of a threat to construct validity in the form of potential experimental bias, either by expectations of the subjects via the Hawthorne effect, or from unintentional experimenter effects. To reduce this threat, participants were blinded to the exact purpose of the experiment until all data was collected, and reliability checks of measurement data were conducted by an assistant blinded to the purpose of the study, but the study could still be limited by experimenter effects. Given a significant result of this investigation, follow-up systematic replication studies will be conducted in other locations with other skilled therapists performing the same experimental treatments.

Threats to internal validity included possible history or maturation effects. History effects are extraneous events prior to post-test that can affect the DV. Maturation effects are changes in the DV resulting from the passage of time, e.g. spontaneous recovery. In AATDs, a control set is used to rule out history and maturation effects.

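### The single before-and-after BDAE reading comparison is meant to assess generalization, but the plan's control set does not cover the BDAE, so a change cannot be separated from spontaneous recovery or retest effects.

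*Combined protocol and SAP*

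**What the plan says.** Outcome Measures and Time Points states that the BDAE "was used as an outcome measure of reading acquisition". On timing, "Pretest reading scores on selected subtests from the BDAE full version were completed prior to baseline A and initiating intervention"; the second administration comes "immediately following completion of intervention to assess generalization to non-trained stimuli". No other BDAE administration is described as part of the outcome assessment.

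Protection against time-related change is described twice. Potential Threats to Internal Validity says: "A control set was used to rule out history and maturation effects". Assumptions and Limitations gives spontaneous recovery as an example of maturation and repeats: "In AATDs, a control set is used to rule out history and maturation effects". Under Independent Variable, that set is "A limited control set using listening to oral reading of the lyrics and silent reading of the written lyrics", with pointing to the lyrics and no music. The measure it serves is set out under Dependent Variables: "The dependent variable was defined as silent reading/comprehension of targeted words/phrases by pointing to words/phrases in a phrase completion exercise without music".

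Time since stroke is among the characteristics to be reported (Reporting Participant Characteristics). The Inclusion/Exclusion Criteria set no lower or upper limit on it.

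**The concern.** The word generalization makes a causal statement: training on lyric phrases improved reading of untrained material. To support it, the design must show that the BDAE change would not have occurred without the training. For the trained phrases, the plan offers repeated measurement and a comparison set. For the BDAE it offers neither, yet the limitations section reads as if the control set dealt with maturation throughout.

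If the text is followed as written, a rise in BDAE reading scores could be reported as generalized improvement when recovery after stroke, or a second sitting of the same test, would explain it equally well. This reaches beyond one report. Sample Size says that only the first two participants are reported here, of a minimum of four and a maximum of ten, and Assumptions and Limitations foresees replication elsewhere after a significant result.

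**Working it through.** The documents give no BDAE effect size, standard deviation, change threshold or power statement, so there is no figure to reproduce. The question is whether the effect can be identified.

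**Inputs**
- BDAE administrations per participant: 2, one before baseline and one after intervention (Outcome Measures and Time Points).
- BDAE control data: no untreated participants, repeated BDAE baseline, interim BDAE or untreated subtest is described.
- Control set: phrases within the phrase completion task (Independent Variable; Dependent Variables).
- Participants: 2 in this report, 4 as the minimum (Sample Size).
- Probability *q* that recovery or retest alone makes a participant's score rise: not in the documents. Assumed 0.8, range 0.5 to 0.9.

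**Step 1: one participant.** Two scores give one change:

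D = post − pre = R + G,

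where R is recovery plus retest gain and G is generalization from the intervention. That is one equation with two unknowns. Any split of D between R and G fits the data equally well, including G = 0.

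**Step 2: several participants.** Each participant contributes the same design row (1, 1). Stacking four such rows still gives a matrix of rank 1 for two unknowns. The mean change estimates mean R + mean G, more precisely but no more separably. For comparison, a second BDAE before intervention would add a row (1, 0) and raise the rank to 2, if R were equal in the two intervals. The plan describes no such test.

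**Step 3: how convincing could a false pattern look?** With G = 0 for everyone and participants independent, the probability that all n improve is qⁿ.

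| q (assumed) | n = 2 | n = 4 |
|---|---|---|
| 0.5 | 0.5² = 0.25 | 0.5⁴ = 0.0625 |
| 0.8 | 0.8² = 0.64 | 0.8⁴ = 0.41 |
| 0.9 | 0.9² = 0.81 | 0.9⁴ = 0.66 |

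Uniform improvement across the sample is thus weak evidence of generalization for any but the smallest q.

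**Step 4: can the control set be borrowed?** It is scored on lyric phrases, not on BDAE items, so it does not estimate R on the BDAE scale. It is also itself a reading condition. And if training did carry over to untrained reading, control phrases could rise as well: a rising control set would fit recovery or generalization, and a flat one would lend support to neither. Whether the control set works for the phrase outcome is a separate matter and is not judged here.

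**The case against.** The strongest reply is that the plan draws no formal inference from the BDAE. The dependent variables listed for analysis are differential percent correct, sessions to mastery and retention. Data Analysis gives the BDAE no test, threshold or decision rule, so in practice it is already descriptive. This is correct, and it limits the point to wording and interpretation. It does not remove it: the stated purpose is still to assess generalization, the BDAE is still called an outcome measure, and no caveat is attached.

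It may also be said that each participant is his or her own control in a single-subject design. That logic works through repeated measurement and comparison between sets, and the BDAE has neither.

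Several stronger readings are tempting but not supported:
- **That the plan uses the BDAE to credit one music condition over the other.** It does not; that comparison rests on the phrase sets. Because treatment proceeds by "alternating procedures on sets 1 and 2 on subsequent treatment visits", the post-test follows both conditions and could not apportion a change between them. This is a limit on interpretation, not an error in the text.
- **That the ICF information shares the flaw.** The plan only says that it is provided before and after, and attaches no claim of generalization or efficacy to it.
- **That a BDAE gain is to be expected without music.** The documents give no recovery or retest figure and no time window after stroke. Participants may be well past early recovery. Recovery is possible, and no more can be said.
- **That the interval between tests can be calculated from the 17 visits mentioned in the plan.** That number belongs to a monitoring definition of normal progress. The intervention phase ends on criterion or discontinuation.

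**Conclusion.** The point holds as a limit on what the BDAE comparison can show. One pretest and one post-test per participant give one change score for at least two unknowns, and this does not improve with four participants or with ten. The plan's safeguard against history and maturation does not extend to this measure, so a BDAE change is not evidence of generalization.

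The identifiability result needs only the testing schedule and the absence of a BDAE control in the text. The probabilities of 0.41 for four participants and 0.64 for two rest on an assumed q of 0.8 and on independence between participants; they illustrate the problem and do not estimate it. The direction and amount of any bias are unknown. Reporting time since stroke gives a reader some context but does not separate the components. The finding concerns an outcome outside the list of analysed dependent variables, and it does not touch the comparison of the two music conditions on the trained phrases.

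**What to change.** 1. In Outcome Measures and Time Points, replace the two descriptions of the BDAE (outcome measure of reading acquisition; assessment of generalization) with descriptive pre/post reading status. State that any change is not attributed to the intervention and is not taken as evidence of generalization.
2. In Assumptions and Limitations, add that the control set applies to the phrase completion task only and does not protect the BDAE comparison from recovery or retest effects.

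For participants already tested, the same wording belongs in the report. No data are lost and no further testing is needed. The cost is a weaker claim.

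Adding a contrast with non-reading BDAE subtests is not recommended as a remedy. It would assume equal recovery across language domains, which the documents do not support, and the conditions include listening to sung or spoken lyrics, so auditory subtests would not be clearly untreated.

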During the baseline (A) all 25 phrases (Appendix C) were tested using the phrase completion task (Appendix D). Both correct responses and participation were verbally reinforced, as is required in an AATD. Results were analyzed by the SLP to ensure that the sets were of equal difficulty for each participant using two different procedures. First, logical analysis of the linguistic characteristics of the phrases was completed, including the number of words, the number of syllables in the words, the number of consonant blends in the words, and the number of contractions. Second, experimental evaluation of the number of error responses in each set during the baseline phase was completed, and without changing the items or responses, the set assignment was manipulated to maximally equate the number of error phrases without significantly changing the equivalency of the linguistic characteristics. One phrase was shifted from set 1 to set 2 during the baseline phase. In the end, the number of error responses on baseline for set 1 was three, for set 2 was two, and for the control set was two.

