- The difference in number of sessions/trials to achieve mastery at each level for each intervention, and the difference in retention at three weeks follow-up were analyzed by comparison of the difference between data points for the control treatment and the two target intervention conditions. After the research design has been completed by a minimum of four subjects, data will be consolidated for group means.

Data Storage

Patient telephone numbers were accessible in the participants' soft file for patient contact while the patient was undergoing speech therapy treatment, as is common practice. On discharge the soft file was stored in the hospital Medical Records Department.

Participants' performance on the phrase completion task was videotaped every third visit using the hospital emergency iPad. The iPad was checked out in the morning before the participant's treatment session. The last treatment trial (for procedural fidelity) and the participant's responses to the phrase completion task (for inter-observer reliability) were recorded and stored in the speech therapy office in the Rehab building until viewed by the assistant in a private location and recorded on the paper reliability data forms. The digital recording was then deleted and the iPad returned. Digital videos did not show participant faces, only hands on the response task were recorded.

Role of the researcher

The primary investigator (PI) pre-selected candidates for participation according to the stated recruitment procedures (above). The rehabilitation manager recruited participants, but the PI obtained informed consent. Given the therapy location, the PI conducted the experimental treatments, making adjustments to the protocol based on preliminary findings as necessary, with IRB approval for any changes. The PI was also responsible for training the (blinded) assistant for reliability checks from videotapes, and interpreting and reporting the data.

Assumptions and Limitations

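### The retention comparison uses the number of items remembered at follow-up with no baseline or end-of-intervention reference, so a difference between conditions cannot be read as retention

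*Combined protocol and SAP*

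**What the plan says.** Outcome Measures and Time Points lists retention as a dependent variable beside daily percent correct and sessions to mastery: "retention of the material (number of items remembered, another simple count which is also a ratio scale". The same section says what is retested: "At four weeks follow-up the trained stimuli from all three interventions was retested to assess retention". That is every trained phrase, not only those learned during the study. Dependent Measures describes the measurement as "percentage correct over time (including follow-up) and trials- or sessions-to-criterion", which supports reading 'remembered' as 'answered correctly'.

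Data Analysis gives the comparison: "the difference in retention at three weeks follow-up were analyzed by comparison of the difference between data points for the control treatment" and the two music conditions. It names no reference score.

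Procedures supplies the starting position. All phrases were tested before intervention ("During the baseline (A) all 25 phrases (Appendix C) were tested using the phrase completion task (Appendix D"), and after sets were adjusted "the number of error responses on baseline for set 1 was three, for set 2 was two, and for the control set was two". Procedures also allows the intervention phase to end with "one acquired and the other discontinued".

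**The concern.** Retention is the part of what was learned that is still present later. It needs at least two reference points: what was known before, and what was known when teaching stopped. A count at follow-up alone adds phrases known from the start to phrases learned and kept, and it does not show phrases learned and lost.

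The plan defends the count as a ratio scale with an absolute zero. With most phrases correct at baseline, keeping nothing of what was learned does not score zero. It scores near the baseline level.

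At stake is the reading of one of the named outcomes. A set with more prior knowledge, or one that learned more, could be reported as better retained. A set with nothing to retain could appear to retain as well as a set that was learned. Data Analysis plans group means after at least four subjects, and pooling the same counts would not separate these components.

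**Working it through.** The plan states no retention figure to reproduce, so the check asks what the count shows when nothing learned is kept.

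**Inputs**
- Total phrases: 25 (Procedures).
- Baseline errors: set 1 = 3, set 2 = 2, control = 2 (Procedures).
- Music set size: 10 each. This is inferred from the 9/10 criterion and the ten songs per set; final sizes are not stated.
- Control set size, by subtraction: 25 − 10 − 10 = 5.

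**Step 1. Phrases already correct at baseline**
- Total errors: 3 + 2 + 2 = 7. Already correct: 25 − 7 = 18, or 18/25 = 72%.
- Set 1: 10 − 3 = 7/10. Set 2: 10 − 2 = 8/10. Control: 5 − 2 = 3/5.
- These are also the follow-up counts if every newly learned phrase is forgotten and no baseline-correct phrase is lost.
- At most 3, 2 and 2 phrases per set can be newly learned, and so retained.

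**Step 2. Sensitivity to the inferred sizes**

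| Set sizes (1 / 2 / control) | Set 1 | Set 2 | Control |
|---|---|---|---|
| 10 / 10 / 5 | 7/10 = 70% | 8/10 = 80% | 3/5 = 60% |
| 9 / 10 / 6 | 6/9 = 67% | 8/10 = 80% | 4/6 = 67% |
| 10 / 9 / 6 | 7/10 = 70% | 7/9 = 78% | 4/6 = 67% |
| 9 / 11 / 5 | 6/9 = 67% | 9/11 = 82% | 3/5 = 60% |
| 11 / 9 / 5 | 8/11 = 73% | 7/9 = 78% | 3/5 = 60% |

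If the reported errors were instead summed over 2 to 5 baseline sessions (an assumption), the starting levels would be higher: 10 − 3/2 = 8.5 to 10 − 3/5 = 9.4 for set 1, and 10 − 2/2 = 9.0 to 10 − 2/5 = 9.6 for set 2.

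**Step 3. What the count hides (illustrative scores)**

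| Case | Baseline | Last visit | Follow-up count | Gain | Change after last visit | New phrases kept |
|---|---|---|---|---|---|---|
| A. Set 1, learned 3, kept 1 | 7 | 10 | 8 | 3 | −2 | 1 of 3 |
| B. Set 1, learned 3, kept 0 | 7 | 10 | 7 | 3 | −3 | 0 of 3 |
| C. Set 2, discontinued, nothing learned | 8 | 8 | 8 | 0 | 0 | none to keep |
| D. Baseline 7, learned 3, kept 2 | 7 | 10 | 9 | 3 | −1 | 2 of 3 |
| E. Baseline 7, learned 2, kept 2 | 7 | 9 | 9 | 2 | 0 | 2 of 2 |

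- A and C tie at 8, although C had nothing to retain.
- B scores below C, although B's set was learned and C's was not.
- D and E start level and tie at 9, although only D lost a phrase. The problem is therefore not only the 3-versus-2 baseline imbalance.

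**Step 4. Comparison with control**
Data Analysis sets control against the music conditions. With 5 and 10 phrases the raw counts have different maxima, so a difference in counts partly reflects set size. Percent correct removes that problem but not the missing reference.

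**The case against.** The strongest reply is that 'remembered' is undefined and might mean learned items still known, and that the planned difference between data points might be a within-condition change. The first reading fits poorly with a retest of all trained phrases and with percentage correct as the follow-up measure. The second is possible grammar, but no starting point for such a change is named. What stands is that the plan's intent is not certain; the missing reference level is.

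Second, a set trained to criterion ends at 9 or 10 of 10, and scores are graphed by session, so its later level can be compared by eye. This stands for sets that meet criterion. It does not help a discontinued set, or the control set, for which no criterion is stated. The control comparison addresses history and maturation, but not this.

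Third, the figures are soft. Set sizes are inferred, one phrase was moved between sets, and only one set of baseline error counts appears although Sample Size reports two participants. This stands: the scores are illustrations.

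Two stronger readings are tempting. A reader might infer that any unlearned set scores 7 or 8 of 10. That figure covers only the music sets; control would start near 3/5.

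A reader might also list every learned-and-kept combination for two sets at criterion and count how often the raw count ranks them differently from the proportion kept. This gives 14 of 35 at the reported baselines. It does not measure the size of the problem. The combinations are unweighted, none is a full reversal, and the proportion is taken as the truth. Follow-up minus last visit, also a reasonable measure, disagrees with that proportion in 8 of the same 35.

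**Conclusion.** The point holds. As written, the between-condition difference in items remembered can present prior knowledge or acquisition as retention. About 18 of 25 phrases had no room to show learning against baseline, and an unlearned set can tie with or exceed one that learned and then lost phrases.

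The 18 of 25 rests on the reported errors being a single-administration count. The per-set scores also rest on sets of 10, 10 and 5. The illustrations assume that baseline-correct phrases stay correct. The definitional gap depends on none of these.

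The documents do not show how often a wrong conclusion would follow, or that any reported retention result is wrong. The change is worth making because the outcome is named, its comparison is planned and the remedy is cheap. It does not affect the acquisition outcomes.

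**What to change.** In Outcome Measures and Time Points and in Data Analysis:

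1. For each set and participant, report percent correct at baseline, at the last intervention visit and at follow-up. Say which visit counts as the last for a discontinued set and for control, since all 25 phrases are tested at each intervention visit.
2. Base the between-condition retention comparison on the change from last intervention visit to follow-up, and always show it beside the gain from baseline. Case C shows why: a change of 0 looks ideal until the gain of 0 is seen.
3. State that a set with no gain has no retention to assess.
4. Call the raw follow-up score 'follow-up level', and do not describe its difference between conditions as a difference in retention.
5. Where phrase-level records allow, also show newly learned phrases still correct over newly learned phrases, as counts. This should not be the only definition, because at the reported errors the denominator is at most three.

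The same edit should reconcile the follow-up time, which is four weeks in Outcome Measures and Time Points and three weeks in Data Analysis.

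Items 1 to 4 need wording and tabulation only, because the set scores are already collected. Item 5 needs phrase-level results linked across visits. The documents describe tallies and do not say whether such records are kept for analysis. The drawback is that, with few items per set, the result stays descriptive and is read mainly after pooling.

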Reliability of the items in the task assessment tool was established using Cronbach's Alpha correlation coefficient once at the beginning of the baseline phase. Inter-observer reliability on the scoring of the tool was determined weekly using the kappa coefficient, also known as Cohen's Kappa. Reliability data was first analyzed for normality/skewness, accuracy, and completeness. Outliers were identified using the Outlier Labeling Rule based on rank and percentile. If data were incomplete, for example if the behavior could not be clearly seen on the digital recording, the corresponding score from the other researcher was eliminated from the reliability determination.

The correlation coefficient chosen is dependent on the scale of measurement of the variables being correlated. For the reliability of the task assessment tool it was used to determine if scores recorded by one researcher were strongly correlated with scores recorded by the other. Scores were recorded as correct versus incorrect, which is a nominal scale. One classic correlation coefficient used with a nominal scale is Cronbach's Alpha, used when both X and Y are dichotomous variables. The assumption that the items of the test are unidimensional cannot be met, meaning that each item measures the same ability on the same scale, because many different mental processes may be used in various combinations from item to item. Cronbach's alpha provides a solution to this problem, so was an appropriate measure of internal consistency (Cronbach, 2004, see p.8). Acceptable values of alpha range from .70 to .90 (Tavakol &

Dennick, 2011). It was predetermined that if alpha was below .70, either the task assessment tool would be revised or the assistant would be re-instructed.

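### Cronbach's alpha is given two incompatible jobs, item reliability and agreement between scorers, under one action rule that cannot tell a poor tool from a poor scorer

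*Combined protocol and SAP*

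**What the plan says.** All of this is in the Data Analysis section of the combined protocol and SAP.

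- Item purpose: "Reliability of the items in the task assessment tool was established using Cronbach's Alpha correlation coefficient once at the beginning of the baseline phase". Later in the section alpha is called a measure of internal consistency.
- Observer purpose: "it was used to determine if scores recorded by one researcher were strongly correlated with scores recorded by the other".
- Scale: "Scores were recorded as correct versus incorrect, which is a nominal scale".
- Reason for choosing alpha: "The assumption that the items of the test are unidimensional cannot be met", after which the text says that alpha "provides a solution to this problem, so was an appropriate measure of internal consistency".
- Range: "Acceptable values of alpha range from .70 to .90".
- Action: "if alpha was below .70, either the task assessment tool would be revised or the assistant would be re-instructed".

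The same section separately assigns inter-observer reliability to Cohen's kappa, determined weekly. Its acceptable kappa² range is .90 to 1.00, and the recording is reviewed again by both researchers if agreement is under 80% or kappa² under .90.

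**The concern.** A reliability coefficient means something only once it is clear what plays the part of cases and what plays the part of components. Between scorers, the phrases are the cases and the two scorers are the components. Between items, persons are the cases and phrases are the components. These are different quantities with different remedies, and the plan attaches one threshold and an either/or remedy to both.

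Alpha is the only stated reliability check on the phrases themselves, since kappa checks scoring. The phrase task supplies percent correct, sessions to mastery and retention (Outcome Measures and Time Points). If the check cannot be interpreted, the plan has no working evidence that the phrases give stable responses, and a low value could send the investigator to the wrong remedy.

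The stated reason for using alpha is also the wrong way round. Alpha can be calculated on items that measure several abilities, but reading it as internal consistency presumes that they measure something in common. It does not repair a failure of that assumption.

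**Working it through.** No observed alpha is reported, so there is no figure to reproduce. The check asks what the stated range does under each reading.

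**Inputs.** 25 phrases are tested (Procedures). Baseline errors are 3 + 2 + 2 = 7, so 18 of 25 are correct (Procedures; the participant is not identified). Alpha range .70 to .90, action below .70, and kappa² .90 to 1.00 (Data Analysis). Two participants are reported (Sample Size).

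**Observer reading.** With two scorers, alpha = 2 × (1 − (var1 + var2) / var(sum)), which equals 4·cov / (var1 + var2 + 2·cov). Assume that scorer 1 records 18 of 25 correct.

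Worked case with one disagreement, scorer 2 recording 17 correct: var1 = .72 × .28 = .2016; var2 = .68 × .32 = .2176; cov = .68 − .72 × .68 = .1904. Alpha = .7616 / .8000 = .952. For kappa, observed agreement is .96 and chance agreement is .72 × .68 + .28 × .32 = .5792, so kappa = .3808 / .4208 = .905 and kappa² = .82.

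Over all ways of splitting the disagreements:

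| Disagreements | Alpha | Against .70 to .90 | Kappa² |
|---|---|---|---|
| 0 | 1.00 | above | 1.00 |
| 1 | .947 to .952 | above | .80 to .82 |
| 2 | .887 to .907 | two of three splits inside | .61 to .67 |
| 3 | .814 to .864 | inside | .43 to .54 |
| 4 | .72 to .824 | inside | .27 to .44 |
| 5 | .59 to .784 | two of six splits inside | below .90 |

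At six and seven disagreements one split each is inside (.747 and .71); at eight, none is. The window moves with the error count. With 2 errors, one disagreement is always inside and four never are. With 9 to 16 errors, two disagreements lie above .90 and three to five are always inside.

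The conflict with kappa does not depend on the error count. With one disagreement in 25, kappa is largest when the scorers record 12 and 13 correct. Chance agreement is then 2 × (12 × 13) / 625 = .4992, so kappa = (.96 − .4992) / (1 − .4992) = .920 and kappa² = .85, below .90. Only perfect agreement meets the kappa² rule, and perfect agreement gives alpha 1.00. On one set of 25 scores, no result satisfies both ranges.

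**Item reading.** Alpha = (k / (k − 1)) × (1 − sum of item variances / variance of totals), with k = 25 and persons as cases.

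- One person, one administration: there is no between-person variance, so alpha is undefined.
- Two persons: let D be the difference in totals and M the number of phrases on which they differ. Each such phrase has variance 1/2 and the totals have variance D²/2, so alpha = (25/24)(1 − M/D²).
- D = 0: undefined.
- D = 2: M = 2 gives (25/24)(.5) = .52; M = 4 gives 0; M = 8 gives (25/24)(−1) = −1.04.
- One person with 7 errors and the other with an assumed 3, 5, 10 or 12: alpha runs from −2.08 to .83, depending on which phrases overlap.

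**The case against.** The best defence is that scoring is already protected. Kappa is the named inter-observer index, it is determined weekly, and its standard is strict: at 7 errors a single disagreement gives kappa² of .80 to .82 and triggers re-review. Participants circle a printed choice, which leaves little room for scoring disagreement. Alpha enters none of the treatment comparisons. The .70 to .90 range directly follows the sentence on internal consistency, so it may have been meant for items only. Much of this stands, and it limits the harm. It does not remove the sentence that uses alpha between researchers, or the either/or remedy.

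A reader might infer four stronger points that the documents do not support.

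- That the plan fails perfect agreement and passes worse data. The acceptable range does exclude 1.00, but the predetermined action applies only below .70, and weekly kappa catches scoring disagreements on recorded sessions.
- That the range accepts exactly two to four disagreements. That window assumes 25 phrases and 7 errors, and is only approximate even then.
- That alpha was computed from one participant. The text does not say how many persons or administrations were used, and two participants are reported.
- That revising the tool would undo the equating of the sets. Alpha is computed at the start of baseline, while equating uses errors made during that phase, and no revision is reported.

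On unidimensionality, it is fair to say that alpha's calculation does not require it. The fault is in offering alpha as the cure, and that part concerns interpretation.

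**Conclusion.** The rule is wrong as written and should be changed, though its reach is limited. One coefficient is given two incompatible meanings, and one threshold leads to two unrelated remedies. As an observer index, its range excludes perfect agreement and cannot be met together with the kappa² range on the same 25 scores. That result assumes two scorers and 25 phrases scored right or wrong, and holds at any error count. As an item index, alpha is undefined for one participant's single administration. For two it is undefined when totals are equal and otherwise too unstable to support a decision. How far this applied in practice is unknown, because the documents do not state the persons or administrations used. No treatment result is shown to be wrong on this account. Correction is still useful: Sample Size requires at least four participants and allows up to ten, and group means are still to come.

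**What to change.** 1. Remove alpha as an observer index. Leave scorer agreement to the kappa and percent agreement already planned, and report both as they stood before any consensus review.
2. Drop the .90 ceiling on alpha.
3. Base no decision on item alpha from one or two participants. If an alpha was computed, state the persons, items and administrations behind it.
4. For the tool, describe for each participant how consistently each phrase is answered right or wrong across baseline probes, where phrase-level results from repeated probes exist.
5. Separate the actions: poor phrase consistency leads to phrase review before set assignment is fixed, and poor scorer agreement leads to re-instruction.
6. Delete the statement that alpha resolves the failure of unidimensionality.

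The cost is small changes of wording and analysis. The phrase-consistency summary depends on phrase-level baseline records having been kept; the documents state neither that they were nor how many baseline probes there were.
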